### **Tertiary/exploratory**

- Evaluate the virologic changes in the treatment arms compared to the control arm as assessed by:
  - Percent of patients with SARS-CoV-2 detectable in nasopharyngeal (NP) sample at days 7, 15, 21, and 29
  - Quantitative SARS-CoV-2 virus in the NP sample at days 7, 15, 21, and 29
  - Development of SARS-CoV-2 variants in NP sample at day 7, 15, 21, and 29
  - Quantitative SARS-CoV-2 virus in blood at days 7, 15, 21, and 29
- To evaluate the cytokine profile and additional biomarkers that may be associated with efficacy and safety associated with sarilumab treatment
- To evaluate the incidence of new or worsening laboratory-confirmed serious secondary infections in the treatment arms as compared to the control arm
- To characterize the concentrations of sarilumab in serum over time
- Patients will not be recalled after discharge for any missing exploratory assessments.

---

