1.3 DETERMINATION OF SAMPLE SIZE

[figure not shown]
The sample size calculations are performed based on the primary endpoint, the time to improvement of 2 points in clinical status assessment from baseline using the 7-point ordinal scale.

Assuming that accrual duration is 3 months (~90 days) with each patient followed for a period of at least 29 days, the proportions of patients with two points improvement from baseline in clinical status assessment at Day 15 are 45% and 70% for placebo and sarilumab, respectively, a total sample size of approximately 400 patients with a 2:2:1 randomization ratio provides at least 90% power for pairwise comparisons between each sarilumab dose (400 mg IV or 200 mg IV; n~160 each) and placebo (n~80), using a log-rank test of superiority at a two-sided significance level of 0.05. Sample size calculation was performed using PASS 14.

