For patients who die, the clinical status recorded on the day of death will be replaced with “1=Death” and this value will be carried forward for all subsequent study days until end of study (Day 60). Death date may be obtained from Adverse Events or Disposition CRFs or phone call at Day 60 (end of study).

For patients who discharge early (other than death), the clinical status recorded on the earliest hospital discharge date will be replaced with 7 (not hospitalized), and this value will be carried forward for all subsequent study days until end of study (Day 60). Hospital discharge information (discharge date and discharge reason) may be obtained from the Discharge Reason eCRF. If there is subsequent hospitalization, the clinical status will not be replaced by 7 after the second hospitalization.

Handling of missing data on clinical status assessment (post-baseline)

For patients who are alive and not discharged (ie, still hospitalized), missing clinical status value (ordinal scale) on a given study day will be imputed using data on the type of oxygen delivery device used by the patient on that day (last type of device used if multiple types were used in a day).

Clinical status = 2 (if using invasive mechanical ventilation or ECMO), or
= 3 (if using non-invasive mechanical ventilation or high-flow nasal cannula), or
= 4 (if using nasal cannula, simple face mask, or non-rebreather face mask) or
= 5 (if not using supplemental oxygen)

Sensitivity analysis

The PPS and ITT will be used for sensitivity analysis of the primary efficacy endpoint, as described above.

Subgroup analyses

Descriptive analyses will be performed on the primary endpoint to summarize the treatment effect of each sarilumab dose versus placebo by the following variables:

- Age (<median, >=median)
- Age group (≥ 18 and < 64 , ≥ 65 and < 84 , ≥ 85 years)
- Sex (Male, Female)
- Race (White, Black or African American, Asian, Other). Note: Japanese will be grouped with Asian, a group with less than 5 patients in any treatment may be grouped with 'Other'
- Ethnicity (Hispanic or Latino, Not Hispanic or Latino)
- Severity of illness (per IRT) (Severe, Critical)
- Severity of illness (as recorded on CRFs) (Severe, Critical)
- Systemic corticosteroids use (per IRT) (Yes, No)
- Systemic corticosteroids use (as recorded on CRFs) (Yes, No)
- Fever status at baseline (Yes, No)
- Pneumonia present based on historical chest X-Ray, CT scan or MRI or lung auscultation (Yes, No)

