- Any symptom of Fever, Cough, or Dyspnea (Yes, No)
- Time from dyspnea onset to baseline (≤ 5 days, > 5 days). Note: patients with no dyspnea will be classified as ≤ 5 days
- SpO₂/FiO₂ ratio (<median, >=median)
- CRP level (<median, >=median)
- Duration of hospitalization prior to first dose (< 7 days, ≥ 7 days);
- Number of study drug administration (1, 2)

Additional subgroups may be added as needed. The treatment effects will be estimated using hazard ratio (sarilumab compared to placebo) in the subgroups using the same analysis model as for the primary efficacy endpoint as described previously (without stratification factor for the stratification-related subgroups). In addition, p-value for the interaction of treatment by subgroup effect will be provided. Graphical presentation of the results (ie, forest plot) for each sarilumab dose versus placebo will also be provided.

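### Interaction p-values for age, SpO2/FiO2 and CRP rest on cut values only; adding a continuous interaction term would recover power if the sarilumab effect changes smoothly with them

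*SAP*

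**What the plan says.** The subgroup list in SAP 2.4.4.1 contains "Age (<median, >=median", "SpO₂/FiO₂ ratio (<median, >=median" and "CRP level (<median, >=median". Each subgroup hazard ratio comes from the primary-endpoint Cox model, which is stratified by randomization stratum except for subgroups built on the stratification factors. The SAP then adds: "In addition, p-value for the interaction of treatment by subgroup effect will be provided". A forest plot is planned for each dose against placebo.

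The SAP introduces the whole set as descriptive. None of it is in the testing hierarchy of SAP 2.4.4.3. The SAP states no interaction size, power or decision rule for these p-values. Age appears a second time in three fixed groups. No continuous-covariate interaction model is planned for any of the three variables.

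**The concern.** Cutting a continuous value at the median treats a patient just above the cut the same as one far above it. If the treatment effect changes gradually with CRP, oxygenation or age, the interaction test on halves ignores the gradient within each half and is weaker than a test on the value already collected. The cut also depends on who happens to be enrolled, so the boundary does not transfer to other data.

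CRP is the variable of most interest. Protocol 2.2 describes it as a marker that sarilumab normalizes, and Protocol 8.6.1 lists it as a pharmacodynamic marker. An exploratory objective reads: "To evaluate the cytokine profile and additional biomarkers that may be associated with efficacy and safety associated with sarilumab treatment". The exploratory comparison of markers with the ordinal scale in SAP 2.4.7 does not list CRP. The median-split row is therefore the only analysis in the SAP that relates baseline CRP to the size of the treatment effect. At stake is a descriptive finding: a real gradient is more likely to go unseen than it needs to be.

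**Working it through.** **Inputs from SAP 1.3.** Allocation is 160 versus 80 per comparison, so the placebo share is 1/3. The assumption is "clinical status assessment at Day 15 are 45% and 70% for placebo and sarilumab, respectively", tested "using a log-rank test of superiority at a two-sided significance level of 0.05", with follow-up of at least 29 days.

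**Inputs assumed, because the documents give none.** The ratio of hazard ratios per SD of the modifier, the modifier's distribution and the shape of the effect.

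**Step 1: hazard ratio and events.** With exponential times, HR = ln(0.30)/ln(0.55) = 2.01. The daily hazards are −ln(0.55)/15 for placebo and −ln(0.30)/15 for sarilumab. The proportions improved by Day 29 are 0.685 and 0.902. Expected events D = 80 × 0.685 + 160 × 0.902 = 199.

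**Step 2: the plan's own power figure.** The SAP says the sample size "provides at least 90% power for pairwise comparisons between each sarilumab dose". Schoenfeld's formula, Φ(√(D × 1/3 × 2/3) × ln HR − 1.96), gives 98.0% at 148 events (Day 15), 99.6% at 199 events (Day 29) and 99.9% at 231 events (90-day accrual plus 29 days). The stated figure is met.

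**Step 3: interaction power.** For a continuous modifier in SD units, the noncentrality is √(D × 2/9) × ln(r), where r is the ratio of hazard ratios per SD. For a median split of a normal modifier it is multiplied by √(2/π) = 0.798, a relative efficiency of 2/π = 0.637. Example at r = 1.4: √(199 × 2/9) = 6.65; 6.65 × ln 1.4 = 2.24, power 60.9%; 2.24 × 0.798 = 1.79, power 43.1%.

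| r per SD | Continuous | Median split | Loss (points) | Loss by simulation |
|---|---|---|---|---|
| 1.1 | 9.7% | 8.0% | 1.7 | not run |
| 1.2 | 22.8% | 16.2% | 6.6 | 6.3 |
| 1.3 | 41.5% | 28.5% | 12.9 | 13.0 |
| 1.4 | 60.9% | 43.1% | 17.9 | 17.6 |
| 1.5 | 76.9% | 57.6% | 19.3 | 21.4 |
| 1.6 | 87.8% | 70.3% | 17.5 | 19.3 |
| 2.0 | 99.6% | 95.7% | 3.9 | not run |

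The simulation used 2,500 unstratified Cox fits per row, censored at Day 29. Its power levels are a little below the formula, but its losses agree. With no interaction, rejection rates were 6.1% (continuous) and 5.6% (split). A second simulation of 1,500 trials per setting gave 5.4% and 5.5%, and losses of 6, 14, 18 and 17 points at log hazard ratio changes of 0.2, 0.3, 0.4 and 0.5 per SD. Extra false positives do not explain the power difference.

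**Step 4: sensitivity.**
- *Events.* At 148 events the loss for r = 1.2 to 1.4 is 4.9 to 15.1 points. Amendment 04 moves later patients to 2:1 without giving the number already randomized. If 200 had been randomized at 2:2:1 (120 of them to 400 mg or placebo) and 200 followed at 2:1, the comparison has 320 patients and 199 × 320/240, or about 266 events. The loss is then 8.8 to 19.3 points.
- *Flatter covariate.* For a uniform modifier the relative efficiency is 0.75 and the largest loss by formula is about 12 points. Simulation gave 8.4 at r = 1.3 and 15.3 at r = 1.5.
- *Step at the median.* For a step scaled to the same SD, the split wins: 37.4% versus 26.6% at r = 1.3, and 72.8% versus 52.0% at r = 1.5.

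**The case against.** The strongest reply is that these p-values decide nothing. The SAP calls the subgroup analyses descriptive, attaches no alpha or decision rule to them and leaves them out of the hierarchy. Median-split rows are a common forest-plot format, and the absence of a cited guideline for them is not a defect. This stands, and it limits the point to an optional improvement.

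A reader might infer that the plan as written gives up a fixed amount of interaction power. The documents do not support that. They contain no interaction size and no covariate distribution, and the loss runs from small to about 19 points, or reverses, depending on what is assumed. SpO2/FiO2 is the doubtful case: SAP 2.5.2 derives FiO2 for several devices from a stepped flow table with caps and sets it to 21% off oxygen. A normal shape cannot be taken for granted there.

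A reader might also infer that a non-significant result would be reported as a uniform effect, or that the CRP split is the planned test of the biomarker objective. No section plans the first reading. On the second, Protocol 8.8 names IL-6, soluble IL-6Rα and SARS-CoV-2 as the samples to be related to clinical response, so the link to CRP is only indirect.

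Some ground is also covered elsewhere. Age has fixed groups, the primary analysis is repeated in severe and critical patients, and further subgroups may be added. None of these uses the continuous value. Power is low either way for modest interactions (16% to 43% split, 23% to 61% continuous at r = 1.2 to 1.4), which is no reason to give up more of it.

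**Conclusion.** The point holds as a cheap improvement. The interaction p-values for age, SpO2/FiO2 and CRP come only from cut values: median splits for all three, plus fixed groups for age. Under a log-linear effect, a roughly normal modifier and about 199 events, the median split loses about 6 to 19 points of interaction power for an assumed ratio of hazard ratios of 1.2 to 1.6 per SD. Outside those conditions the figure changes as shown in the working. The calculations ignore the randomization strata that the SAP's model would use. The primary and key secondary analyses, their error control and their power are unaffected.

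**What to change.** In SAP 2.4.4.1, after the sentence on interaction p-values, add a pre-specified analysis for baseline age, SpO2/FiO2 and log CRP:

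- Fit the stratified Cox model with treatment, the continuous baseline value and their product, for each dose versus placebo, and report the p-value of the product term.
- Report the hazard ratio with its confidence interval at the 25th, 50th and 75th percentiles of the baseline value.
- Add a simple linearity check, for example a spline with knots fixed in advance, and state how a CRP value that cannot be logged is handled.
- Keep the median-split rows in the forest plot as description, and label the new p-values descriptive and outside the hierarchy.

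The SAP on file (version 2, 05-May-2020) predates Amendment 04, so the change could go into a revision made for that amendment, before the primary database lock. The cost is SAP wording and one extra model per variable and dose comparison (3 × 2 = 6) on data already collected. The downside is a shape assumption: if the true effect is a step near the median, the continuous test is the weaker one. That is why the split rows should stay and the linearity check should accompany the new p-value.

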## 2.2 BACKGROUND

Coronavirus disease (COVID-19) is caused by severe acute respiratory syndrome coronavirus 2 (SARS-CoV-2), a protein-enveloped RNA virus (4) related to severe acute respiratory syndrome coronavirus (SARS-CoV) and Middle East respiratory syndrome-related coronavirus (MERS-CoV)(5). COVID-19 presents with influenza-like symptoms (fever, cough, dyspnea, nausea, vomiting, diarrhea) and radiographic features of diffuse pneumonia (5, 6, 7, 8, 9), with more severe cases characterized by neutrophilia, lymphopenia, thrombocytopenia, elevations in acute phase reactants and inflammatory cytokines (8), including IL-6 (9). Over 25% of patients develop acute respiratory distress during the second week of hospitalization (7). Acute, life-threatening respiratory injury induced by coronavirus infection is associated with an over-exuberant cytokine release (also known as “cytokine storm”) (10, 11). Case series of patients afflicted with SARS-CoV and MERS-CoV pneumonia indicate that elevations in IL-6 and other pro-inflammatory cytokines are correlated with clinical and radiographic severity (12, 13) and that in SARS-CoV pneumonia, peak viral load precedes peak IL-6 concentration and subsequent peak radiographic severity (14). As of 14 March 2020, there are many efforts to develop vaccines, anti-virals, and therapeutics against COVID-19, but none have yet demonstrated meaningful efficacy.

Clinical management of hospitalized patients with COVID-19 includes supportive therapy: supplemental oxygen therapy to target SpO2, empiric antimicrobials, empiric neuraminidase inhibitor for treatment of influenza when there is local circulation, and intensive care as required (WHO, 2020) (15).

Both SARS-CoV-2 (16, 17) and SARS-CoV (18) exploit angiotensin converting enzyme II (ACE2) to infect pulmonary and intestinal epithelial cells (18, 19, 20) and activate NF-kappa B upregulation of proinflammatory cytokines such as IL-6 (21, 22). SARS-CoV infected pulmonary epithelial cells, pneumocytes, and macrophages (Mφ) produce elevated levels of IL-6, MCP-1, TGF-β1, and other proinflammatory cytokines and chemokines (23).

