## 5 STUDY POPULATION

Prospective approval of protocol deviations to recruitment and enrollment criteria, also known as protocol waivers or exemptions, is not permitted.

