#### Type of participant and disease characteristics

I 02. Hospitalized for less than or equal to 7 days (or documentation of a plan to admit to the hospital if the patient is in an emergency department) with illness of any duration with evidence of pneumonia by chest radiograph, chest computed tomography or chest auscultation (rales, crackles)

AND meets at least one of the following prior to randomization (patients meeting more than one criterion will be categorized in the most severely affected category).

Participants who are with a:

- Severe disease:

Requires supplemental oxygen administration by nasal cannula, simple face mask, or other similar oxygen delivery device (ie. increase in oxygen requirement following COVID infection).

- Critical disease:

- Requires supplemental oxygen delivered by non-rebreather mask or high-flow nasal cannula

OR

- Use of invasive or non-invasive ventilation

OR

- Requiring treatment in an intensive care unit.

I 03. Laboratory-confirmed SARS-CoV-2 infection (eg, by PCR), or other commercial or public health assay in any specimen within 2 weeks prior to randomization and no alternative explanation for current clinical condition.

I 04. Willing and/or able to comply with study-related procedures/assessments

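### Three descriptive subgroup definitions in SAP 2.4.4.1 (hospital stay before dosing, time since dyspnea onset, age bands) are badly specified and should be reworded

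*SAP*

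**What the plan says.** SAP 2.4.4.1 lists 17 subgroup variables for the primary endpoint and calls the analyses descriptive. For each it plans a hazard ratio per dose versus placebo, an interaction p-value and a forest plot. Three entries matter here.

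- **Hospital stay.** The variable is "Duration of hospitalization prior to first dose", split at under 7 versus 7 or more days. Protocol 5.1, criterion I 02, admits patients "Hospitalized for less than or equal to 7 days (or documentation of a plan to admit to the hospital" from an emergency department), "with illness of any duration with evidence of pneumonia by chest radiograph" or other chest findings. Protocol Section 5 adds that approving deviations from the entry criteria in advance, "also known as protocol waivers or exemptions, is not permitted".
- **Time from dyspnea onset to baseline.** The split is 5 days or less versus more than 5 days. The SAP adds: "Note: patients with no dyspnea will be classified as" 5 days or less.
- **Age group.** The bands are 18 to under 64, 65 to under 84, and 85 or over. SAP 2.1.1 uses the same bands for the demographic summary.

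In the same list, age, CRP and SpO2/FiO2 are each split at the median.

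**The concern.** The hospital-stay cut sits on the eligibility ceiling. Screening and baseline may fall within 24 hours of each other (Protocol 1.3, footnote 2), so little time need pass between the eligibility check and the first dose. Nearly all patients should then land on one side of the cut.

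The dyspnea rule places patients who have no onset date in a group defined by a recent onset. The age bands, followed literally, drop two full years of age.

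What is at stake is how the forest plot and the interaction p-values are read. A null interaction from a very small upper group, or from a diluted lower group, could be taken as evidence that timing makes no difference. Patients aged 64 or 84 would be missing from the age-group rows. SAP 2.4.5 also promises selected safety summaries by age group without redefining the bands, so the gap may carry over there.

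**Working it through.** **Inputs.** SAP 1.3 and Protocol 9.2 give two-point improvement by Day 15 of 45% (placebo) and 70% (sarilumab), about 160 and 80 patients per pairwise comparison, two-sided 0.05, and at least 29 days of follow-up. The primary analysis is at Day 29 (SAP Section 4). The share of patients at 7 or more days in hospital is not in the documents. I assume 2% to 25%; a flat spread over days 0 to 7 gives 1/8 = 12.5%.

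**The plan's own figure first.** Constant hazards are −ln(0.55)/15 = 0.0399 and −ln(0.30)/15 = 0.0803 per day, so HR = 2.01. Events by Day 15 are 0.45 × 80 + 0.70 × 160 = 148. Schoenfeld power is Φ(√(148 × 1/3 × 2/3) × ln 2.01 − 1.96) = 98%. Counting events to Day 29 gives 199 events and 99.7%. Both agree with the stated power of at least 90%.

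**Hospital-stay cut.** Extending the same hazards to Day 29 gives event probabilities of 1 − exp(−0.0399 × 29) = 0.685 (placebo) and 1 − exp(−0.0803 × 29) = 0.903 (sarilumab). For a share f in the upper group:

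- SE(log HR) = √(1/(160f × 0.903) + 1/(80f × 0.685))
- CI factor = exp(1.96 × SE)
- Interaction variance = variance in the upper group + variance in the lower group; power is for HR 2.01 in one subgroup and 1.0 in the other.

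At f = 12.5%: events 18.1 and 6.9; SE = √(1/18.1 + 1/6.9) = 0.449; factor = exp(0.88) = 2.4.

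| Share at ≥7 days (assumed) | Sarilumab / placebo | Events | CI factor | Interaction power |
|---|---|---|---|---|
| 2% | 3 / 2 | 4 | 9.0 | 9% |
| 5% | 8 / 4 | 10 | 4.0 | 16% |
| 12.5% | 20 / 10 | 25 | 2.4 | 31% |
| 25% | 40 / 20 | 50 | 1.86 | 48% |
| 50% (median split) | 80 / 40 | 100 | 1.55 | 60% |

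The normal approximation is rough in the top two rows, where placebo has fewer than three events.

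**Dyspnea rule.** Suppose the true HR is 2.01 in patients with recent dyspnea and 1.0 in those with none, and that the latter make up a share d of the group at 5 days or less. The group HR is then about exp((1 − d) × ln 2.01): 1.88 at d = 10%, 1.63 at 30%, 1.42 at 50%. Both d and the absence of effect are assumptions.

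**Age bands.** SAP 2.5.1 computes age as consent date minus birth date, divided by 365.25. Ages from 64 to just under 65, and from 84 to just under 85, satisfy none of the three bands. No assumption is needed.

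**The case against.** The strongest reply is that these are three lines among 17 descriptive subgroups, outside the testing hierarchy of SAP 2.4.4.3. The effect-modification question that the objectives do pose is efficacy by clinical severity. SAP 2.4.4.1 and 2.4.4.2 address it by repeating the primary and key secondary analyses in severe and in critical patients. This stands, and it limits the weight of the point.

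Four stronger readings are tempting, and the documents do not support them.

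- **That these subgroups were meant to test disease stage.** A reader might infer this from Protocol 2.2, which says "Over 25% of patients develop acute respiratory distress during the second week of hospitalization". That is natural history; neither document states an early-versus-late treatment hypothesis or gives these subgroups that purpose. Since I 02 sets no limit on illness duration, days in hospital would be a poor measure of stage wherever it is cut.
- **That the upper hospital-stay group is empty.** Day-7 patients satisfy both rules, and the subgroup clock runs to first dose. The SAP does not say how stay is counted. If it added one day, as SAP 2.4.4 does for time-to-event durations, calendar days 6 and 7 would both qualify: 2 in 8 under a flat spread, the 25% row above.
- **That the dyspnea comparison is lost.** The group above 5 days contains only patients with a known onset. The other group is diluted, not uninterpretable.
- **That the intervals are wider still.** Counting events only to Day 15 gives factors of 2.9, 5.4 and 1.7 for 12.5%, 5% and a median split, but the primary analysis is at Day 29.

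The 160/80 split also predates closure of the 200 mg arm. If closure came at 200 randomized (80/80/40) and the other 200 were split 2:1 (133/67), with the total kept at 400, the pair would be about 213/107 and the 12.5% factor about 2.1. That is an assumption and does not change the conclusion.

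Finally, age is also split at the median, so patients aged 64 and 84 are not lost from every age analysis. The band wording is still wrong.

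**Conclusion.** The point holds as a specification defect in three descriptive subgroups. The age bands are wrong as written, in two places. The hospital-stay cut is poorly placed against the entry cap and is likely to give a sparse upper group. Over assumed shares of 5% to 12.5% its hazard ratio would carry a CI factor of about 4.0 to 2.4, against about 1.55 for a median split. The dyspnea rule dilutes the group at 5 days or less by an amount that the documents do not allow one to calculate.

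These sizes rest on the design event rates extended exponentially to Day 29, on 160/80 patients, and on shares that are assumed. Even a median split gives only about 60% power for an interaction as large as HR 2.01 versus 1.0, so the correction makes the hospital-stay subgroup readable, not confirmatory. The primary test, alpha, sample size and key secondary endpoint are untouched.

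**What to change.** In SAP 2.4.4.1:

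- Cut hospital stay before first dose at the blinded pooled median, in the form already used for age, CRP and SpO2/FiO2. This also removes the dependence on whether a day is added to the count.
- Report patients with no dyspnea as a separate category, and compute the interaction for 5 days or less versus more than 5 days only among patients with an onset date.
- Use age bands 18 to <65, 65 to <85 and ≥85, and make the same change in SAP 2.1.1.

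The cost is SAP wording before database lock. All variables are already collected: SAP 2.1.1 lists dyspnea yes/no, time from dyspnea onset and stay before dosing at baseline. Two downsides: the no-dyspnea category may be small and reportable only descriptively, and if stay is recorded in whole days, ties will make the median split only roughly even.
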